## **Experimental design**

The project will be a descriptive cross-sectional study.

A total of 55 adult participants will be recruited from the Case Western Reserve Orthodontics Clinic, based on the sample size calculation with a power of 80%. Inclusion criteria: current adult patients in the Case Western Reserve Orthodontics Clinic, ages 20-75, willingness to give informed consent

and participate in study, owner of a smartphone, and ability to return the Belun Ring and complete follow-up questionnaire. Exclusion criteria: age <20, currently or with history of taking blood pressure medication, currently undergoing transverse or anterior-posterior orthodontic correction, and currently pregnant or trying to become pregnant.

Participants will provide informed consent and will be instructed on the steps of the study. Demographic information will be collected, including a participant identifier, age of participant, and sex of participant. The use of the Belun Ring will be demonstrated, and they will be instructed on use of the Sleep Cycle app. They will complete the NOSE Score Questionnaire, STOP-Bang Questionnaire, Insomnia Severity Index, PROMIS Sleep Disturbance Questionnaire, and the Epworth Sleepiness Scale (ESS).

Data collected from the STOP-Bang Questionnaire includes positive/negative responses to: snoring, tired, observed, pressure, BMI >35, age over 50, neck size large, male gender, and the resulting OSA risk assessment of low, intermediate, or high.

Data collected from the NOSE Questionnaire includes positive or negative responses to: nasal congestion or stuffiness, nasal blockage or obstruction, trouble breathing through my nose, trouble sleeping, unable to get enough air through my nose during exercise or exertion, and the resulting classification of severity of nasal obstruction (mild, moderate, severe, extreme).

Data collected from the Insomnia Severity Index include difficulty falling or staying asleep, problem with waking up too early, satisfaction level with current sleep pattern, noticeability of subject's sleep problem to others, and amount of distress regarding current sleep habits.

Data collected from the PROMIS Sleep Disturbance Questionnaire includes level of agreement with statements about the subject's ability to fall asleep, quality of sleep, amount of sleep, level of satisfaction with their sleep, ability to stay asleep throughout the night.

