The Epworth Sleepiness Scale collects information regarding the subject's likelihood of falling asleep during the following activities: sitting and reading, watching television, sitting in public, sitting in a car, lying down to rest, sitting and talking to someone, sitting quietly after lunch without alcohol, and while sitting in a car stopped in traffic.

The participants are then instructed to wear the Belun Ring for seven nights and simultaneously use the Sleep Cycle app.

Data collected from the Belun Ring includes the Respiratory Event Index (REI) (derived from total sleep time, heart rate variability, and O2 saturation changes), Sleep Efficiency (time participant is asleep divided by total time in bed), stress level, mean spO2 (%), Sleep Score (bAHI, Belun Ring's version of AHI), REM sleep (percentage), minimum spO2 (%), mean pulse rate (bpm), percent of time below 90% oxygen saturation, and total sleep time (minutes).

The Sleep Cycle app will collect the subject's time asleep, stages "Awake, Sleep, and Deep Sleep," sleep regularity, time to bed, time woken up, time in bed, sleep efficiency, heart rate, and time snoring. It also will record audio while the subject is asleep. During the night, the subject's

smartphone will be placed on their nightstand. The subjects also have the option to add “sleep notes” to give additional information about their night of sleep, for example, if they were feeling sick or if they exercised right before bed.

The subjects will return to the Case Western Reserve Orthodontic Clinic for their next orthodontic adjustment appointment. The subjects will return the Belun Ring to the clinic and we will download the data. The Sleep Cycle Score Report from each night will be collected by either sharing via WhatsApp, an encrypted messaging service, or recording the data points manually into an Excel spreadsheet.

Subjects will then complete a Follow-Up Questionnaire. They will record the dates they used the devices during sleep. Subjects will also indicate whether they had a “normal” night of sleep, or if they were experiencing sickness, allergies, or any other sleep disruptions that may have affected the data collected. They will also indicate whether they have a bed partner.

Participants will be referred for further evaluation, if needed.

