### **Statistical Analysis Design**

Out of the seven nights of sleep studied, the five with the longest night of sleep will be used for analysis. The values from those five nights will be averaged for each patient.

Descriptive statistics will be applied to the data, in order to determine reliability and consistency among different data collection methods, since similar variables are collected by different means. Correlation of data collected by different methods will be performed in order to cross examine and further validate results.

We will compare the accuracy of the response to the STOP-Bang question “Do you snore?” to audio data from the Sleep Cycle app. We will also compare the amount of snoring reported to the nasal obstruction score of the NOSE questionnaire. We will compare the distribution of the STOP-Bang questionnaire results (low/medium/high risk of Obstructive Sleep Apnea) to the distribution of results from the sensors. We will compare the agreement in recommendation for follow-up between the STOP-Bang Questionnaire and the sensors. Last, we will collect the percentage of people in the adult orthodontic clinic that should be referred for further evaluation for potential intervention.

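### Both snoring comparisons leave out the bed-partner answer the study collects, so unless the app separates sleepers, a partner's snoring can be counted as the participant's

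*Combined protocol and SAP*

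**What the plan says.** Under Experimental design, the participant's "smartphone will be placed on their nightstand" overnight. The app's outputs are listed as the participant's own data ("The Sleep Cycle app will collect the subject's time asleep", with snoring time later in the same list), and of sound the section says "It also will record audio while the subject is asleep". At the return visit the follow-up questionnaire covers the dates of device use and anything that disturbed sleep. Of participants it adds: "They will also indicate whether they have a bed partner".

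Under Statistical Analysis Design there are two snoring comparisons. The first sets the STOP-Bang snoring answer against the app, with accuracy judged by reference "to audio data from the Sleep Cycle app". The second reads: "We will also compare the amount of snoring reported to the nasal obstruction score of the NOSE questionnaire". STOP-Bang asks about snoring as yes or no and yields no amount, so the app's snoring time is the natural reading of the second comparison, though the sentence does not say so.

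The section does not mention bed-partner status as a stratum, covariate, exclusion or sensitivity analysis, and gives no rule for deciding whose snoring was recorded. The background paragraph on smartphone apps lists what Sleep Cycle measures and does not claim that it distinguishes two people.

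**The concern.** In the first comparison the app is the yardstick for self-report. A microphone on a nightstand can pick up anyone in the room. If the app does not separate sleepers, the yardstick for a partnered participant may reflect two people. Poor self-report and a snoring partner then look the same in the results.

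In the second comparison, a partner's minutes have no evident reason to follow the participant's own nasal obstruction, so they act as noise and pull the correlation towards zero. Averaging the five longest nights does not help when the partner is there every night.

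Later repair may not be possible. The plan collects nightly score reports and describes no transfer of the audio itself. The background says the app deletes audio after 20 nights, and the interval to the next adjustment visit is not given. The bed-partner answer is therefore the one planned piece of information that bears on this error, and it has no stated use.

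**Working it through.** **1. The plan's own figure.** The only related number is the sample size: "A total of 55 adult participants will be recruited from the Case Western Reserve Orthodontics Clinic". The plan attributes that number to a calculation at 80% power. It cannot be reproduced, because the significance level, effect size and test are not given. Assuming a correlation tested two-sided at 5%, Fisher's z gives a detectable r of tanh((1.960 + 0.842)/√(55 − 3)) = 0.37. The point does not depend on this; it only gives a scale for step 4.

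**2. Accuracy of the snoring item.** Assumptions, none from the documents:
- 33 of 55 truthfully answer No.
- 50% have a partner in the room (range 40-70%).
- 40% of those partners register as snoring (range 20-50%).
- The app is otherwise correct and does not separate sleepers.

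Wrongly scored answers = truthful No × share partnered × share of partners snoring.

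| Case | Wrongly scored | Accuracy shown by a perfect item |
|---|---|---|
| Low | 33 × 0.4 × 0.2 = 2.6 | (55 − 2.6)/55 = 95% |
| Middle | 33 × 0.5 × 0.4 = 6.6 | (55 − 6.6)/55 = 88% |
| High | 33 × 0.7 × 0.5 = 11.6 | (55 − 11.6)/55 = 79% |

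Cross-check with 30% of participants snoring and the same middle partner rates: agreement = 0.30 + 0.70 × (1 − 0.5 × 0.4) = 0.86. The app-positive share is 0.30 + 0.14 = 0.44, so chance agreement is 0.30 × 0.44 + 0.70 × 0.56 = 0.524. Kappa is (0.86 − 0.524)/(1 − 0.524) = 0.71, although both measures are otherwise perfect.

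**3. The opposite error.** A non-snorer who wrongly answers Yes is scored as correct if the partner snores. With f = share partnered × share of partners snoring, the net fall in accuracy is f × (truthful No − wrong Yes)/55. In the middle case f = 0.20. With no wrong Yes the fall is 0.20 × 33/55 = 12 points. With an assumed 5 wrong Yes it is 0.20 × (33 − 5)/55 = 10 points.

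**4. Dilution of the NOSE correlation.** Assumptions: 40% of participants snore; minutes among snorers have mean 60 and SD 40, for participants and partners alike; partner minutes are independent of the participant's own minutes and NOSE score. The mean square is 40² + 60² = 5200.
- Own variance: 0.4 × 5200 − (0.4 × 60)² = 1504.
- Partner variance, middle case (f = 0.20): 0.2 × 5200 − (0.2 × 60)² = 896.
- Factor: √(1504/(1504 + 896)) = 0.79.

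Over the ranges in step 2 (f = 0.08 to 0.35), partner variance is 393 to 1379 and the factor 0.89 to 0.72. With 30-70% partnered and 20-60% of partners snoring (f = 0.06 to 0.42), it is 0.91 to 0.70. A true r of 0.37 would be seen as 0.37 × 0.79 = 0.29. Under the step 1 assumptions, power at 55 falls from 80% to about 58.5%.

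**5. Size of the no-partner group.** If 30%, 50% or 70% are partnered, about 38, 28 or 17 of 55 remain. The detectable r (as in step 1) is 0.44, 0.51 or 0.63.

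**The case against.** The strongest reply is that the plan is a short outline and does not say that all recorded sound belongs to the participant. The bed-partner question comes straight after one on disturbances that could affect the recordings, so the investigators may well intend to use it. A reader might infer a deliberate rule of pooling everyone; the text does not support that. A reader might also infer that contamination is certain. It depends on how the app attributes sound, and a brief feature list is not evidence that it cannot separate sleepers. Both limits stand, and the point is conditional for that reason. What remains is that the plan, followed as written, neither separates sleepers nor uses the answer.

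Other stronger readings also fail. The error in accuracy is not purely downward (step 3). A factor of 1/√2 = 0.71 for the NOSE correlation would need partner minutes to vary as much across the sample as participants' own; the middle rates give 0.79, and 0.71 lies near the severe end.

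Nor do the documents support making the no-partner group the main estimate. It may be small, and it selects people with no bed partner to tell them whether they snore, while the stated objective is the adult clinic population. Finally, the study is descriptive, and the ring-based results do not depend on snoring audio. That limits the weight of the point without removing it.

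**Conclusion.** The point holds in conditional form. Both snoring comparisons omit a variable that the study already collects and that bears directly on whether the app's reading belongs to the participant. If the app does not separate sleepers, the middle illustration has about 6.6 of 55 answers wrongly scored, 88% apparent accuracy for a perfect item (95% to 79%), and a NOSE correlation shrunk by about 0.8 (roughly 0.7 to 0.9). Every rate behind these figures is assumed; they show that the effect could matter, not how large it will be. The NOSE part also takes the amount of snoring to mean app minutes; the STOP-Bang part does not need that reading. This is a cheap improvement to a descriptive study, not a flaw that undermines it.

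**What to change.** In Statistical Analysis Design:
- Report both snoring comparisons separately for participants with and without a bed partner, alongside the pooled result.
- Name the no-partner group as a planned sensitivity analysis.
- State how recorded snoring is attributed, and limit conclusions about self-report accuracy accordingly.

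In Experimental design, add to the follow-up form, for each device date, whether another person slept in the room, ideally noted each night rather than recalled at the visit. The present item records only having a partner, not presence on a given night or whether the partner snored, so stratifying on it removes part of the error. The nightly entry would also let partner-free nights of partnered participants be used.

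The cost is a few sentences in the analysis section and one column on an existing form. The price in precision is smaller groups (about 17 to 38 of 55 without a partner if 70% to 30% are partnered) and wider intervals. Differences between the groups need care in reading, because having a partner may also affect how well people know whether they snore.
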